5.4.2. Endpoint Events and Definitions – Maternal Participants

The study endpoints for maternal participants employ the event definitions in [Table 9](#).

Table 9. Endpoint Events and Definition in Maternal Participants

Study Endpoint/Assessment	Study Definition
Maternal medically attended visit	The maternal participant reports a visit with a healthcare provider (eg, outpatient or inpatient visit, emergency room, urgent care, or home visit).
MA-RTI visit for maternal participant	A medically attended visit AND 1 or more of the following RTI signs and symptoms: 
 • New or increased sore throat • New or increased cough • New or increased nasal congestion • New or increased nasal discharge • New or increased wheezing • New or increased sputum production • New or increased shortness of breath

Abbreviations: MA-RTI = medically attended respiratory tract illness; RTI = respiratory tract illness.

6. ANALYSES AND SUMMARIES

6.1. Primary Endpoints

6.1.1. Primary Efficacy Endpoints – Infant Participants

6.1.1.1. RSV-Positive MA-LRTI (as Confirmed by the EAC) Occurring Within 90 Days, 120 Days, 150 Days, and 180 Days After Birth

6.1.1.1.1. Main Analysis

- Estimand strategy: Hypothetical.
- Analysis set: Evaluable efficacy – infant ([Section 4](#)).
- Analysis methodology: VE will be analyzed using a conditional exact test based on the binomial distribution of the number of disease cases in the RSV vaccine group, given the total number of cases in both groups.
- Intercurrent events and missing data: All postdiscontinuation or postviolation observations will be censored; such events include the infant receiving palivizumab or another monoclonal antibody targeting RSV and the infant receiving transfusions of more than 20 mL/kg of any blood products at ≤ 180 days of age.
- For each group, the number (n), percentage, and 95% CI of RSV-positive MA-LRTI cases occurring within 90 days, 120 days, 150 days, and 180 days after birth, as confirmed by the EAC, will be presented for each group. Severe MA-LRTI cases are a subset of MA-LRTI cases, and all severe MA-LRTI cases will also be considered MA-LRTI cases.

- VE compared to placebo along with the corresponding 100(1- alpha)% CI (adjusted for the interim) will be presented. This will be based on raw numbers of cases and also with an adjustment for any differences in follow-up time. See [Section 5.1](#) for testing procedures.
- Kaplan-Meier curves showing accrual of cases for this endpoint over 180 days will be presented.

6.1.1.1.2. Supplementary Analysis

The main analysis will also be performed based on the mITT efficacy infant population. Other supportive analyses will address the impact of specific issues, as follows.

Impact of palivizumab administration: A supportive analysis of the primary endpoint will be performed to address the potential intercurrent event of palivizumab administration via a composite estimand strategy. For this analysis, the population will be the mITT efficacy infant set. The endpoint analyzed will be the occurrence of either MA-LRTI due to RSV (as defined for the main analysis) or receipt of palivizumab. VE with respect to this outcome will be estimated in the same way as for the main analysis.

Imputed missing swab analysis: Where MA-LRTI and severe MA-LRTI visits have no accompanying valid central or local NAAT test results, positive or negative results will be imputed as described in [Section 5.3.3](#). If any such events were adjudicated, only those that were confirmed by the EAC as MA-LRTI or severe MA-LRTI will undergo imputation. The imputed RSV-positive cases will be added to the per-protocol cases and VE estimated in the same way as for the main analysis.

Expanded swab analysis: Where some evidence of RSV positivity exists from MA-LRTI and severe MA-LRTI visit swabs, any test indicating positivity for RSV will be accepted and used to define MA-LRTI cases whenever the clinical symptoms qualify. Examples of positive swab results that do not count for the primary endpoint definition, but will be counted in this analysis, are local non-NAAT tests, central laboratory PCR tests from samples taken outside the protocol-specified window, and centrally-tested swabs that exceeded the documented stability testing duration but were positive. Where events were adjudicated, the committee's decision on the event as MA-LRTI or severe MA-LRTI will be used; if not adjudicated, the event will be assessed according to the protocol criteria for each event. VE including these additional RSV-positive cases will be estimated in the same way as for the main analysis.

Combined analysis of Phase 2b/Phase 3 efficacy data: In order to provide additional summaries of RSVpreF VE, combined data from Studies C3671003 and C3671008 (this study) will be generated for descriptive purposes only. Data on incidence of MA-LRTI and severe MA-LRTI will be combined using the Phase 3 endpoint definitions. The 4 RSVpreF groups in the C3671003 study will be combined. VE will be estimated by simple pooling of the study data without stratification/weighting, and 95% CI provided. The analysis will be considered final after all infants in both studies have reached 180 days of age.

6.1.1.2. Severe MA-LRTI Due to RSV (as Confirmed by the EAC) Occurring Within 90 Days, 120 Days, 150 Days, and 180 Days After Birth**6.1.1.2.1. Main Analysis**

- Estimand strategy: Hypothetical.
- Analysis set: Evaluable efficacy – infant ([Section 4](#)).
- Analysis methodology: VE will be analyzed using a conditional exact test based on the binomial distribution of the number of disease cases in the RSV vaccine group, given the total number of cases in both groups.
- Intercurrent events and missing data: All postdiscontinuation or postviolation observations will be censored; such events include the infant receiving palivizumab or another monoclonal antibody targeting RSV and the infant receiving transfusions of more than 20 mL/kg of any blood products at \leq 180 days of age. For each group, the number (n), percentage, and 95% CI of cases of severe MA-LRTI due to RSV occurring within 90 days, 120 days, 150 days, and 180 days after birth (as confirmed by the EAC) will be presented for each group.
- VE compared to placebo along with the corresponding $100(1 - \alpha)\%$ CI (adjusted for the interim) will be presented. This will be based on raw numbers of cases and also with an adjustment for any differences in follow-up time. See [Section 5.1](#) for testing procedures.
- Kaplan-Meier curves showing accrual of cases for this endpoint over 180 days will be presented.

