5.3.3. Efficacy Data

Cases that qualify as MA-LRTI events based on clinical signs and symptoms but do not have a valid RSV swab result will be identified. Sensitivity analyses of the primary endpoints will be done under various assumptions about the missing swab results. In each scenario, cases with imputed positive RSV results will be added to the confirmed RSV-positive cases and vaccine efficacy in the augmented set of cases analyzed.

Based on a blinded review of swab results at the end of February 2022, approximately 22% of all swabs from MA-LRTI events with valid central lab results cases proved to be RSV-positive. Thus, a minority of the missing results are expected to be truly RSV-positive, and imputation scenarios will include:

- Missing swab results are assumed to be positive in the same proportion (by vaccine group) as the nonmissing swab results in MA-LRTI events (missing-at-random assumption).
- For the vaccine group, missing swab results are assumed to be positive in higher proportions than the nonmissing swab results in MA-LRTI events, while in the placebo group missing swab results are assumed to be positive in the same proportion as the nonmissing swab results in MA-LRTI events (missing-not-at-random assumption). A range of higher vaccine group positivity rates will be assumed.

Multiple imputations will be performed to randomly assign missing swab results. SAS PROC MI will be used to generate 500 imputed data sets for each scenario. Mean and median VE across imputations, and the proportion of imputations with VE lower bound >20% will be reported.

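### The missing-swab imputation ignores RSV results already observed, so most events whose only RSV evidence is a non-qualifying positive are drawn negative under missing-at-random

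*SAP*

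**What the plan says.** Section 6.1.1.1.2 of the SAP sets out two supportive analyses for swab problems.

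The imputed missing swab analysis covers MA-LRTI and severe MA-LRTI visits that "visits have no accompanying valid central or local NAAT test results, positive or negative results will be imputed as described in" Section 5.3.3. Its one filter concerns the clinical event: among adjudicated events, "only those that were confirmed by the EAC as MA-LRTI or severe MA-LRTI will undergo imputation".

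The expanded swab analysis says that "any test indicating positivity for RSV will be accepted and used to define MA-LRTI cases whenever the clinical symptoms qualify". Its examples of positives outside the primary definition "are local non-NAAT tests, central laboratory PCR tests from samples taken outside the protocol-specified window", and central swabs that were positive after the documented stability time.

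Section 5.3.3 supplies the imputation rates. It notes that "approximately 22% of all swabs from MA-LRTI events with valid central lab results cases proved to be RSV-positive" and infers that a minority of missing results are truly positive. Under the first scenario (missing at random, MAR), "Missing swab results are assumed to be positive in the same proportion (by vaccine group) as the nonmissing swab results in MA-LRTI events". Under the second (missing not at random, MNAR) the placebo arm keeps its observed rate, and for the vaccine arm "A range of higher vaccine group positivity rates will be assumed". Each scenario uses 500 imputed data sets. The report gives mean and median VE and the proportion of data sets with a VE lower bound above 20%.

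For severe MA-LRTI, Section 6.1.1.2.2 names the imputation and the pooled Phase 2/3 analysis. It does not name the expanded swab analysis.

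**The concern.** The two sets of events overlap. An event with a positive local non-NAAT test and no valid NAAT result meets the criterion for imputation, and nothing removes it from the imputation set or fixes its status. The same holds for out-of-window or past-stability central PCR positives if these are classed as not valid, which the SAP does not settle.

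The 22% rate is a reasonable prior for an event with no RSV information. It is a poor one for an event with a positive antigen or PCR result. A MAR assumption is meant to hold given the observed data, and here a strongly predictive observation is set aside.

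The analysis exists to show whether events without a valid swab could change the conclusion. If the events with other RSV evidence are split less favourably than the confirmed cases, the imputation dilutes the evidence that would show it. No planned analysis both counts these positives and imputes the events whose status is truly unknown.

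**Working it through.** **Inputs from the SAP.** Pooled positivity P = 0.22 (Section 5.3.3); design VE 60% (Section 7.2); 1:1 allocation and a target of 124 cases (Section 2.2). The 22% is an observed blinded rate given without counts, so it cannot be re-derived.

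**Assumptions.** Equal numbers of non-RSV MA-LRTI events in the two arms. The number and split of events with only a non-qualifying positive are not given and are varied below.

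**Step 1: positivity by arm.** Per placebo RSV event, let there be (1 − VE) vaccine RSV events and b non-RSV events in each arm. Setting pooled positivity to P gives b = (2 − VE) × (0.78/0.22)/2. Placebo positivity is 1/(1 + b) and vaccine positivity is (1 − VE)/(1 − VE + b). At VE 60%, b = 1.4 × 3.545/2 = 2.482, so placebo is 1/3.482 = 28.7% and vaccine is 0.4/2.882 = 13.9%.

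**Step 2: chance that such an event is drawn negative under MAR** (1 − positivity):

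| Assumed VE | Vaccine | Placebo |
|---|---|---|
| 0% | 78% | 78% |
| 20% | 80% | 76% |
| 40% | 83% | 74% |
| 60% | 86% | 71% |
| 80% | 91% | 68% |

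Under MNAR at VE 60%, the arm difference vanishes when the vaccine rate is multiplied by 28.7/13.9 ≈ 2.07, and it reverses beyond that. Above about 3.6 times (50%), vaccine-arm events are no longer mostly drawn negative.

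**Step 3: effect on VE.** Take 35 v 89 confirmed cases (total 124, VE = 1 − 35/89 = 60.7%) and add events with only a non-qualifying positive. The MAR column adds expected draws at 13.9% and 28.7%; for 10 v 10 that is 1.4 and 2.9, giving 36.4 v 91.9.

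| Such events, vaccine v placebo | Counted as cases | VE if counted | VE as planned (MAR) | Gap |
|---|---|---|---|---|
| 3 v 7 | 38 v 96 | 60.4% | 61.1% | 0.7 points |
| 5 v 5 | 40 v 94 | 57.4% | 60.5% | 3.1 points |
| 10 v 10 | 45 v 99 | 54.5% | 60.4% | 5.9 points |

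**Step 4: effect on the reported proportion above 20%.** The exact interval used here reproduces the 6 v 37 row of Table 11: VE 84% (27%, 98%). Take an assumed 10 v 30 severe cases plus 3 v 3 such events, and a 97.55% interval (the 1-sided 2.45% of Section 7.2, doubled to 4.9% and halved between endpoints). Counting the events gives 13 v 33 and a lower bound of 16%. MAR imputation at the Step 1 rates puts the lower bound above 20% in about 84% of data sets. The counts and the even split are chosen to show that the readout can change, not to predict that it will.

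**The case against.** The strongest objection is that relabelling individual events need not bias VE. The exact test uses only case totals by arm, and the imputation set also contains RSV-negative events, some of which are drawn positive. Take a missing pool with 4 vaccine and 10 placebo true positives and 24.8 non-RSV events per arm. At the Step 1 rates the imputation adds 28.8 × 0.139 = 4.0 and 34.8 × 0.287 = 10.0, which matches the truth. This stands. A reader might infer that the analysis necessarily pulls VE toward the main estimate; that requires a pool that departs from MAR, and Section 5.3.3 has a separate MNAR scenario.

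The even splits in Step 3 are also adverse by construction, since they assume no efficacy among these events. With 3 v 7, close to the ratio of the confirmed cases, the gap is under 1 point.

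For MA-LRTI, the expanded swab analysis counts these events, so an unfavourable split would show there. Treating an event differently in two supportive analyses is not in itself a contradiction. For severe MA-LRTI this answer is weaker: the expanded swab paragraph mentions severe visits, but it defines MA-LRTI cases, and Section 6.1.1.2.2 does not list that analysis.

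Finally, these results fall outside the primary definition and may include false positives, so calling the events known positives would go too far. That argues against certainty. It does not support giving them the same chance as an event with no test.

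**Conclusion.** The point holds as a limited defect in a supplementary analysis. As written, events whose only RSV evidence is a non-qualifying positive are imputed as if nothing were known about them, and about 78% are drawn negative under MAR at the pooled rate. The split of 86% vaccine and 71% placebo assumes VE 60% and equal non-RSV MA-LRTI.

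A reader might infer that such events are always lost more often from the vaccine arm. The documents do not support that: it holds under MAR with VE above 0, and the MNAR scenario, whose range is not stated, can remove or reverse it. Nor do they show that the analysis will report false robustness, because the number and split of these events are unknown. The illustrated shift in VE runs from under 1 point to about 6 points.

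Membership in the imputed set is clear for local non-NAAT positives. For out-of-window and past-stability central PCR it depends on how validity is classed. Primary cases, alpha and success criteria are untouched. The change is still worth making, because conditioning on an observed and highly predictive result is better than discarding it, and the reported proportion with a lower bound above 20% can depend on it.

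**What to change.** Amend Sections 5.3.3, 6.1.1.1.2 and 6.1.1.2.2 so that the imputation conditions on observed RSV results, for both primary endpoints:

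- Hold events with a positive result under the expanded-swab criteria positive in all 500 data sets of each scenario.
- Treat non-qualifying negative results symmetrically: hold them negative, or enter the result as a predictor in the imputation model.
- Impute at the scenario rates only events with no RSV result of any kind.
- State whether out-of-window and past-stability central results count as valid for this purpose.

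The symmetry matters. Holding positives while imputing everything else at the unchanged rate would overcount. In the pool used under the objection, if all 14 true positives had other evidence, it would give 4 + 24.8 × 0.139 = 7.4 vaccine and 10 + 24.8 × 0.287 = 17.1 placebo positives, about 24.5 in all against a true 14.

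The cost is a short change of wording, a positive-result flag already needed for the expanded swab analysis, and a matching flag for negative results. VE in this sensitivity analysis may look slightly less favourable.

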6.1.1.2.2. Supplementary Analysis

The main analysis will also be performed based on the mITT efficacy infant population. Furthermore, an analysis with missing swab imputation and the efficacy analysis on combined data from Phases 2 and 3 similar to those mentioned in [Section 6.1.1.1.2](#) will be performed for this endpoint as well.

6.1.2. Primary Safety Endpoints: Infant Participants**6.1.2.1. Specific Birth Outcomes**

- Analysis set: Safety – infant ([Section 4](#)).
- Analysis methodology: Descriptive summary statistics.
- Intercurrent events and missing data: Analysis will be carried regardless of whether an intercurrent event occurs.

- For each group, the number and proportion of participants with each specific birth outcome (see [Appendix 1](#) for the list of specific birth outcomes) will be presented by vaccine group. In addition, the difference in proportions and associated 2-sided 95% CI between the vaccine group and the placebo group will be presented.

6.1.2.2. AEs Within 1 Month of Age

- Analysis set: Safety – infant ([Section 4](#)).
- Analysis methodology: Descriptive summary statistics for Tier 3 events; difference and 95% CI between the vaccine group and the placebo group for Tier 2 events. No Tier 1 events are identified.
- Intercurrent events and missing data: For participants who discontinue, all collected data will be included; missing AE dates will be imputed as described in Pfizer’s Vaccine Statistics Rulebook.
- For each group, the number of participants with AEs within 1 month of age (30 days) (n), percentage, and 95% CI will be presented for any AE, each SOC, and each PT within each SOC, by vaccine group. For AEs classified as Tier 2 events, the difference in proportions and associated 2-sided 95% CI between the vaccine group and the placebo group will be presented.

6.1.2.3. SAEs and NDCMCs From Birth Through 6 and 12 Months of Age

- Analysis set: Safety – infant ([Section 4](#)).
- Analysis methodology: Descriptive summary statistics.
- Intercurrent events and missing data: For participants who discontinue, all collected data will be included; missing AE dates will be imputed as described in Pfizer’s Vaccine Statistics Rulebook.
- For each group, the number of participants with SAEs and NDCMCs through 6 and 12 months of age (n), percentage, and 95% CI will be presented (in separate outputs) for any event, each SOC, and each PT within each SOC, by vaccine group.

6.1.2.4. SAEs and NDCMCs From Birth Through 24 Months of Age (for Infants Born to Maternal Participants Enrolled During First Year of the Study)

- Analysis set: Safety – infant ([Section 4](#)).
- Analysis methodology: Descriptive summary statistics.
- Intercurrent events and missing data: For participants who discontinue, all collected data will be included; missing AE dates will be imputed as described in Pfizer’s Vaccine Statistics Rulebook.

- For each group, the number of participants with SAEs and NDCMCs (in separate outputs) through 24 months of age (n), percentage, and 95% CI will be presented for any event, each SOC, and each PT within each SOC, by vaccine group.
- For each group, the number of participants with SAEs and NDCMCs (in separate outputs) between 12 and 24 months of age (n), percentage, and 95% CI will be presented for any event, each SOC, and each PT within each SOC, by vaccine group.

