2.1.4.2. Primary Safety Estimands – Infant Participants

- **Percentage of infant participants with specific birth outcomes.**

This estimand includes the following 4 attributes:

- Population: Infant participants born to maternal participants receiving 1 dose of investigational product.
- Variable: Presence/absence of specific birth outcomes (see [Appendix 1](#)).
- Intercurrent event(s): No intercurrent events to be considered.
- Population-level summary: Percentage of infant participants with specific birth outcomes in each group.

- **Percentage of infant participants having AEs from birth to 1 month of age.**

This estimand includes the following 4 attributes:

- Population: Infant participants born to the maternal participants receiving 1 dose of investigational product.
- Variable: Presence/absence of AEs from birth to 1 month.

- Intercurrent event(s): For participants who discontinue, all collected data will be included; missing AE dates will be imputed as described in Pfizer's Vaccine Statistics Rulebook.
- Population-level summary: Percentage of infant participants with AEs from birth to 1 month of age in each group.
- **Percentage of infant participants with SAEs and NDCMCs from birth through 6 and 12 months.**

This estimand includes the following 4 attributes:

- Population: Infant participants born to the maternal participants receiving 1 dose of investigational product.
- Variable: Presence/absence of SAEs and NDCMCs from birth through 6 and 12 months of life.
- Intercurrent event(s): For participants who discontinue, all collected data will be included; missing AE dates will be imputed as described in Pfizer's Vaccine Statistics Rulebook.
- Population-level summary: Percentage of infant participants with the event of interest during the first 6 and 12 months of life in each group.
- **Percentage of infant participants with SAEs and NDCMCs from birth through 24 months.**

This estimand includes the following 4 attributes:

- Population: Infant participants born to the maternal participants enrolled during the first year of the study and who received 1 dose of investigational product.
- Variable: Presence/absence of SAEs and NDCMCs from birth through 24 months of life.
- Intercurrent event(s): For participants who discontinue, all collected data will be included; missing AE dates will be imputed as described in Pfizer's Vaccine Statistics Rulebook.

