An immediate AE is defined as any AE that occurred within the first 30 minutes after administration of the investigational product for maternal participants.

An NDCMC is defined as a disease or medical condition, not previously identified, that is expected to be persistent or otherwise long-lasting in its effects.

An ADE is defined as an AE related to the use of an investigational medical device. These events will be captured separately and reported in relation to the administration of the investigational product.

A 3-tier approach will be used to summarize AEs for maternal participants and infant participants. Under this approach, AEs are classified into 1 of 3 tiers. Different analyses will be performed for different tiers (see [Section 6.6.1](#)).

Tier 1 events: These are prespecified events of clinical importance and are maintained in a list in the product's Safety Review Plan. There are currently no Tier 1 events defined.

Tier 2 events: These are events that are not Tier 1 but are “common”. A MedDRA PT is defined as a Tier 2 event if there are at least 1% in at least 1 group.

Tier 3 events: These are events that are neither Tier 1 nor Tier 2 events.

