6.1.3.4. SAEs Throughout the Study

- Analysis set: Safety – maternal ([Section 4](#)).
- Analysis methodology: Descriptive summary statistics.
- Intercurrent events and missing data: For participants who discontinue, all collected data will be included; missing AE dates will be imputed as described in Pfizer's Vaccine Statistics Rulebook.

- For each group, the number of participants with SAEs throughout the study (n), percentage, and 95% CI will be presented for any event, each SOC, and each PT within each SOC, by vaccine group.

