9. APPENDICES

Appendix 1. Specific Birth Outcomes

The specific birth outcomes of interest for this study are listed below:

- AEs categorized as AESIs in the database
- Neonatal death
- Congenital malformations/anomalies
- Other neonatal problems
- Final Apgar score (at either 1, 5, or 10 minutes) less than 7

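### No vaccine-placebo difference is prespecified for the SAE and NDCMC primary safety endpoints, although the SAP gives one for birth outcomes and Tier 2 AEs

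*SAP*

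**What the plan says.** **SAEs and NDCMCs.** Section 6.1.2.3 (infants, 6 and 12 months) sets the output by vaccine group, for both kinds of event, as a count of infants "through 6 and 12 months of age (n), percentage, and 95% CI will be presented (in separate outputs) for any event", and then by SOC and PT. Section 6.1.2.4 repeats this "through 24 months of age (n), percentage, and 95% CI will be presented for any event", and again for the window from 12 to 24 months. For mothers, Section 6.1.3.4 presents "the number of participants with SAEs throughout the study (n), percentage, and 95% CI will be presented for any event", SOC and PT. The estimand summaries in Sections 2.1.4.2 and 2.1.4.3 match; for infants through 6 and 12 months the summary is "Percentage of infant participants with the event of interest during the first 6 and 12 months of life in each group". No contrast between arms appears in any of these places.

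**Other primary safety endpoints.** Section 6.1.2.1 (specific birth outcomes) is also labelled descriptive, yet there "the difference in proportions and associated 2-sided 95% CI between the vaccine group and the placebo group will be presented". Appendix 1 shows that these outcomes include neonatal death, congenital malformations and "AEs categorized as AESIs in the database". Section 6.1.2.2 (infant AEs within 1 month) plans, "For AEs classified as Tier 2 events, the difference in proportions and associated 2-sided 95% CI between the vaccine group and the placebo group"; Section 6.1.3.3 does the same for mothers.

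**The tier rule.** Section 3.5.1 applies a 3-tier approach to the AEs of mothers and infants: "A MedDRA PT is defined as a Tier 2 event if there are at least 1% in at least 1 group". Section 6.6.1 says that the primary AE endpoint analyses using that approach are set out in Sections 6.1.2 and 6.1.3, and that multiple comparisons will not be adjusted for.

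**General methods.** Section 5.2.1 allows a CI for the difference in percentages of binary endpoints wherever it is appropriate. It names Clopper-Pearson for single proportions and Miettinen-Nurminen for differences.

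**The concern.** The trial randomises mothers 1:1, and the safety question that randomisation answers is how much more or less often an event occurs on RSVpreF than on placebo. An interval for each arm describes that arm. It does not give an interval for the excess, which is what shows how large an excess the data rule out. For any SAE and any NDCMC, over windows that run to 24 months in infants and to the 6-month postdelivery visit in mothers, the planned tables leave that quantity to the reader.

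The plan is also uneven. It makes the comparison for two kinds of primary safety endpoint and leaves it out for others of the same binary type, without a reason. If the gap is filled later, the choice of which differences to show would be made after the results are known.

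**Working it through.** **1. The sections side by side**

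| Primary safety endpoint | SAP section | Per-arm %, 95% CI | Difference, 95% CI |
|---|---|---|---|
| Specific birth outcomes | 6.1.2.1 | number and proportion only | yes |
| Infant AEs within 1 month | 6.1.2.2 | yes | Tier 2 PTs |
| Infant SAEs, NDCMCs to 6 and 12 months | 6.1.2.3 | yes | not stated |
| Infant SAEs, NDCMCs to 24 and over 12-24 months | 6.1.2.4 | yes | not stated |
| Maternal local reactions, systemic events | 6.1.3.1, 6.1.3.2 | yes | not stated |
| Maternal AEs within 1 month | 6.1.3.3 | yes | Tier 2 PTs |
| Maternal SAEs | 6.1.3.4 | yes | not stated |

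The descriptive label does not explain the pattern, because birth outcomes carry it and still get the difference. Tier 2 depends on PT frequency alone, so an SAE PT reaching 1% in an arm meets the definition; Sections 6.1.2.3, 6.1.2.4 and 6.1.3.4 nevertheless contain no tier analysis.

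**2. An illustration of what a difference CI adds**

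The SAP states no event rate, margin or power for SAEs or NDCMCs, so there is no figure of its own to reproduce.

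Inputs: 1:1 allocation, about 6900 pairs, rising to as many as 10,000 mothers (Section 2.2). That is 6900/2 = 3450 or 10,000/2 = 5000 per arm. Placebo rates of 1% to 20% are assumed.

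Methods, both from Section 5.2.1:
- Clopper-Pearson for x events in n: lower limit = the 0.025 quantile of Beta(x, n - x + 1); upper limit = the 0.975 quantile of Beta(x + 1, n - x).
- Miettinen-Nurminen for difference d: z(d) = (p1 - p2 - d) / sqrt{[q1(1 - q1)/n1 + q2(1 - q2)/n2] x N/(N - 1)}, where p1 and p2 are the observed vaccine and placebo proportions, N = n1 + n2, and q1 = q2 + d are the constrained maximum likelihood estimates. The limits are where z(d) = +1.96 and -1.96.

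For each placebo count, I take the smallest vaccine count at which the difference CI excludes zero, and the smallest at which the two per-arm intervals no longer overlap.

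One case by hand, 3450 per arm, 172 placebo events (5%):
- 210 vaccine events: d = 38/3450 = 1.10 points; pooled rate 382/6900 = 5.54%; standard error 0.551 points; z = 2.00, so zero is excluded. The CI is 0.02 to 2.19 points.
- 209 vaccine events: z = 1.95, so zero is not excluded.
- The per-arm intervals separate first at 227 events: 55/3450 = 1.59 points.
- Ratio of the two excesses: 55/38 = 1.45.

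| Per arm | Placebo events (assumed rate) | Difference CI excludes 0 at (excess, points) | Intervals separate at (excess, points) | Ratio |
|---|---|---|---|---|
| 3450 | 34 (1%) | 53 (0.55) | 62 (0.81) | 1.47 |
| 3450 | 69 (2%) | 94 (0.72) | 107 (1.10) | 1.52 |
| 3450 | 172 (5%) | 210 (1.10) | 227 (1.59) | 1.45 |
| 3450 | 345 (10%) | 396 (1.48) | 419 (2.14) | 1.45 |
| 3450 | 690 (20%) | 757 (1.94) | 786 (2.78) | 1.43 |
| 5000 | 50 (1%) | 72 (0.44) | 83 (0.66) | 1.50 |
| 5000 | 250 (5%) | 295 (0.90) | 315 (1.30) | 1.44 |
| 5000 | 500 (10%) | 561 (1.22) | 588 (1.76) | 1.44 |
| 5000 | 1000 (20%) | 1080 (1.60) | 1115 (2.30) | 1.44 |

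The ratio stays between 1.43 and 1.52.

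**The case against.** The case for the plan is substantial. The safety objectives are to describe, Section 6.6.1 calls safety analysis generally exploratory, and the estimands are percentages within each group, so the outputs match what was asked. Local reactions and systemic events are handled in the same way. Section 5.2.1 leaves room for a difference CI, and the table shells, which are prepared separately, may contain one. No stated inference becomes wrong.

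Part of this stands: the point concerns reporting and prespecification, and the SAP does not rule the comparison out. But the permission in Section 5.2.1 does not say whether SAEs and NDCMCs qualify, while other endpoint sections say so explicitly where a difference is meant. A descriptive aim is no bar either, as Section 6.1.2.1 shows.

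Three stronger readings are tempting and fail:
- **That the most serious events are never compared between arms.** Neonatal death, congenital malformations and AESIs are compared as birth outcomes.
- **That the Tier 2 comparison covers only non-serious events.** Tier 2 is set by PT frequency; serious PTs that reach 1% within 1 month are included.
- **That the plan judges safety by whether intervals overlap.** It contains no such rule. Section 5.2 requires numerators and denominators, so a reader can compute the difference from the planned tables.

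**Conclusion.** The point holds as a moderate gap. Sections 6.1.2.3, 6.1.2.4 and 6.1.3.4 prespecify per-arm summaries only, while neighbouring primary safety endpoints get a difference with a 95% CI and the SAP says that the primary AE endpoints follow the tier approach. What remains without a stated comparison is any SAE and any NDCMC at every time point, and individual SAE and NDCMC terms over the long windows.

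The factor of about 1.4 to 1.5 shows how much less sharply two per-arm intervals display an imbalance than the difference CI does. It rests on assumed placebo rates of 1% to 20%, on 3450 to 5000 per arm, and on a reading rule that the SAP does not contain. Those arm sizes do not apply to the 24-month and 12-24-month analyses, which are restricted to infants of mothers enrolled in the first year. The efficacy analysis is unaffected.

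**What to change.** Add to Sections 6.1.2.3, 6.1.2.4 and 6.1.3.4 wording such as: *For any SAE and (infants) any NDCMC, and for each PT reaching 1% in either group (Tier 2), the difference in proportions, RSVpreF minus placebo, will be shown with its 2-sided 95% Miettinen-Nurminen CI (Section 5.2.1). These intervals are descriptive and carry no multiplicity adjustment.* Add the same difference to the matching population-level summaries in Sections 2.1.4.2 and 2.1.4.3.

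The any-event rows go slightly beyond what Sections 6.1.2.2 and 6.1.3.3 state for AEs, where the difference is given for Tier 2 terms; they are worth having because the totals are the primary safety endpoints. PTs below 1% stay with counts and percentages, as under Tier 3.

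The cost is SAP wording and one more column in existing tables, using a method already specified. The downside is more unadjusted intervals, some of which will exclude zero by chance. Section 6.6.1 already accepts this.
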